10 STATISTICAL CONSIDERATIONS

10.1 Sample Size Determination

10.1.1 Dose Escalation

During the dose-escalation trial, the sample size at each dose in these arms depends on observed toxicity and posterior inference.

Up to approximately 78 participants are planned to be enrolled for Part 1 (dose escalation) and clinical pharmacology substudy: approximately 30 participants for the dose-escalation phase, with up to 24 additional participants in Part 1 for additional characterization of the safety, PK, and pharmacodynamic profile of BMS-986242, and approximately 24 participants for the clinical pharmacology substudy (including food effect). [Appendix 7](#) provides additional details for the operating characteristics of the BLRM for monotherapy and BLRM-copula for combination therapy based on doses from 25 mg; an addition of 12.5 mg is expected to provide similar operating characteristics..

For the food effect assessment, the sample size is not based on statistical power for comparison but on consideration of the precision of the estimates of geometric means of C_{max} and AUC(0-T) of BMS-986242.

For a sample size of 6 participants, there is an 80% probability for the 90% confidence interval to be within 79.6% to 125.7% of the point estimate of the geometric mean for C_{max} and within 80.4% to 124.4% of the point estimate of the geometric mean for AUC(0-T). This calculation assumes that log(C_{max}) and log(AUC[0-T]) of BMS-986242 are normally distributed with a standard deviation (SD) of 0.23 and 0.22, respectively, as estimated from a study of a related compound.

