2 MODEL SETUP FOR BMS-986242 AND NIVOLUMAB COMBINATION

2.1 Methodology Description for Combination Therapy

Toxicity profiles of both BMS-986242 monotherapy and nivolumab monotherapy will be incorporated to develop the combination model framework. A copula-type model will be used to cover all general combination cases, including additive and synergistic effects. The combination of the 2 treatments will be explored using a Bayesian hierarchical model by utilizing the toxicity profiles of the single agents as prior marginal profiles for the combination. The following copula-type model⁴ will be used to describe the probability p_{ij} of toxicity when dose level i of agent A and dose level j of agent B are administered in combination:

$$p_{ij} = 1 - \exp\left(-\left[\{-\log(1 - p_i^m)\}^{1/\gamma_1} + \{-\log(1 - q_j^n)\}^{1/\gamma_1}\right]^{\gamma_1}\right),$$

where p_i is the prespecified best guess toxicity probability for agent A, q_j is the prespecified best guess toxicity probability for agent B, m and n characterize the individual drug effect, and γ_1 characterizes the drug-drug interactive effect.

The joint toxicity framework models the toxicity rates of both agents as well as their interaction effects in a 7-parameter hierarchical model, where each monotherapy dose-toxicity relationship will be characterized by a 2-parameter BLRM model (see [Section 1.1](#)). There are 3 additional parameters for the copula-type model, 1 for each agent (m and n) as well as 1 for the interaction term (γ_1). A dose-toxicity surface will be characterized for different dose combinations of these 2 agents.

As there are currently no historical data or prior knowledge to indicate how much information is to be borrowed for each of the single agents, parameters m and n are both set to be 1, meaning borrowing 100% of the information from the 2 agents. The above formula is then simplified into a 5-parameter model as follows:

$$p_{ij} = 1 - \exp\left(-\left[\{-\log(1 - p_i)\}^{1/\gamma_1} + \{-\log(1 - q_j)\}^{1/\gamma_1}\right]^{\gamma_1}\right).$$

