2.2 Prior Specification for Combination Therapy

2.2.1 Marginal Prior for BMS-986242

Posterior information on $\log(\alpha_1)$ and $\log(\beta_1)$ from the monotherapy Lead in will be used as marginal BMS-986242 prior for combination with nivolumab. This prior information is not prespecified and will be continuously updated when additional DLT information from the monotherapy is available. In the simulation (see Section 3, the prior of BMS-986242 as described in Section 1.2.1 (Table 1) is used for illustration purposes because no real-time DLT data are available at this time.

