3.2.1 Operating Characteristics of BLRM for Monotherapy

Three scenarios were investigated by selecting (1) dose-DLT relationship derived by prior, (2) narrow safety window in order to explore how EWOC limits the risk of exposing participants from a toxic dose level, and (3) all doses above the target toxicity (Table 4).

Table 4: Simulation Results of BLRM for Monotherapy

Scenario	BMS-986242 Dose (mg)	25	50	100	200	400	600	MTD not selected (%)	Fitted MTD	Toxicity Observed (%)	Avg # Pts
By Prior	% DLT	2	4	7	13	22	30				
	% MTD	0	0	2.6	25.9	46.5	24.7	0.2	598.8	17.6	18.4
	# Pts	3.1	0.2	0.8	4.2	6.6	3.5				
	# DLTs	0.0	0.0	0.0	0.1	1.3	1.2				
Narrow Safety Window	% DLT	2	4	7	13	22	60				
	% MTD	0.2	0.3	1.7	29.7	62.9	4.8	0.4	546.6	19.6	18.3
	# Pts	3.1	0.2	0.9	4.7	7.3	2.1				
	# DLTs	0.1	0.0	0.0	0.6	1.6	1.3				
All High	% DLT	40	50	60	70	75	80				
	% MTD	8.8	3.9	1	0.2	0	0	86.1	28.7	54.8	7.7
	# Pts	4.6	1.5	0.7	0.3	0.6	0				
	# DLTs	1.8	0.7	0.4	0.2	0.4	0				

Note: % DLT = true DLT rate; % MTD = proportion of the dose selected as the MTD; # Pts = average number of participants by adjusting for skipped dose level where the true toxicity rate is below the target rate; # DLTs = average number of DLTs by adjusting for skipped dose level where the true toxicity rate is below the target rate; Fitted MTD = fitted MTD at 33% as the target toxicity rate; % toxicity observed = average proportion of DLTs given the doses were tried

Doses with true target toxicity within the target toxicity interval [16%, 33%)

Abbreviations: Pts = participants.

The average sample size was no more than 20 participants. The results for the scenarios of narrow safety window and all high show how the EWOC principle limits the risk of exposing participants from a toxic dose level. Overall, the scenarios illustrated above demonstrate that the model performs well in the hypothetical scenarios investigated by correctly identifying the MTD at least 62% of the time while limiting participants from receiving excessive/unacceptable toxic dose levels.

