3.2.2 Operating Characteristics of BLRM-copula for Combination Therapy

Three hypothetical scenarios were investigated: (1) additive joint toxicity; (2) toxicity rates 25% higher than the additive scenario; (3) toxicity rates 50% higher than the additive scenario (Table 5).

Table 5: Simulation Results of BLRM-Copula for Combination

Scenario	BMS-986242 Dose	25	50	100	200	400	600	MTD not selected (%)	Fitted MTD	Toxicity Observed (%)	Avg # Pts
Additive	% DLT	12	14	17 ^a	23 ^a	32 ^a	40				
	% MTD	2.7	5.7	23.6	24.6	23.6	9.8	10	464.7	24.3	19.5
	# Pts	3.6	3.2	4.7	3.6	2.4	2.2				
	#DLT	0.5	0.4	0.7	0.8	0.7	0.9				
25% Higher	% DLT	15	18 ^a	21 ^a	29 ^a	40	50				
	% MTD	5.5	8.7	26.4	29.8	12.9	2.6	14.1	357.2	27.7	17.7
	# Pts	3.8	3.2	4.5	3.5	1.7	1.1				
	#DLT	0.6	0.6	0.9	0.9	0.7	0.6				
50% Higher	% DLT	18 ^a	21 ^a	26 ^a	34	48	60				
	% MTD	7.9	10.7	29.5	24.5	5.4	0.2	21.8	291.7	31.7	15.5
	# Pts	3.9	3.2	4.1	2.8	0.9	0.6				
	#DLT	0.7	0.7	1.0	0.9	0.5	0.3				

^a Doses with true target toxicity within the target toxicity interval [16%, 33%]

Note: % DLT = true DLT rate; % MTD = proportion of the dose selected as the MTD; #DLT = average number of DLTs; MTD not selected = dose was below lowest dose or above highest dose; Fitted MTD = fitted MTD at 33% as the target toxicity rate; Toxicity observed = Average proportion of DLTs out of all simulated trials; # Pts = average number of participants

The average sample size was around 20 participants. The results show how the EWOC principle limits the risk of exposing participants from unacceptable toxic dose levels. Overall, the scenarios illustrated above demonstrate that the model performs well by correctly identifying the MTD ranging from 49% to 72% in the hypothetical scenarios investigated while limiting participants from receiving unacceptable toxic dose levels.

[figure not shown]
4 INTERIM MONITORING CASE STUDY TO ILLUSTRATE PROVISION OF DOSE RECOMMENDATIONS DURING DOSE ESCALATION

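### Table 5 and the 49% to 72% claim in Appendix 7 do not describe the combination model the trial will run: they leave out the lead-in data, start at 25 mg and include no all-toxic scenario

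*Combined protocol and SAP*

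**What the plan says.** All references are to the combined protocol and SAP.

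- **Planned model.** Appendix 7, Section 2.2.1: posterior information on the two BMS-986242 parameters "from the monotherapy Lead in will be used as marginal BMS-986242 prior for combination with nivolumab", updated as lead-in DLTs accrue. Section 2.1 states no discount: "parameters m and n are both set to be 1, meaning borrowing 100% of the information from the 2 agents".
- **Simulated model.** Section 2.2.1 adds that in the simulation the Table 1 prior "is used for illustration purposes because no real-time DLT data are available at this time".
- **Dose range.** Section 3.1 simulates 25 to 600 mg. Section 5.1 starts the trial at 12.5 mg. Section 10.1.1 covers the gap by saying that "an addition of 12.5 mg is expected to provide similar operating characteristics".
- **Scenarios.** Table 4 (monotherapy) includes a case with every dose above target. Table 5 (combination) has three scenarios, each with three doses inside the 16% to 33% target interval.
- **Conclusion drawn.** Section 3.2.2 reports the model as "correctly identifying the MTD ranging from 49% to 72% in the hypothetical scenarios investigated" and adds: "The results show how the EWOC principle limits the risk of exposing participants from unacceptable toxic dose levels".

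**The concern.** The lead-in cannot see toxicity that arises only when nivolumab is added. Clean lead-ins pull the BMS-986242 curve down. At full weight, later combination DLTs must then be explained by the nivolumab margin (prior centre 1/(1 + e^3.269) = 3.7% at its reference dose) or by the interaction parameter, so the overdose rule can react more slowly. A simulation without lead-in data cannot show this. The lower-of-two dose rule in Section 5.1.2.1 gives limited protection here, because a clean lead-in also leaves the monotherapy model permissive.

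At stake is whether the published operating characteristics can support reliance on the model's recommendations in a first-in-human trial that has no Data Monitoring Committee.

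**Working it through.** **1. The plan's own figures.** Sum of Table 5 % MTD over the doses flagged as in target:
- Additive: 23.6 + 24.6 + 23.6 = 71.8%
- 25% Higher: 8.7 + 26.4 + 29.8 = 64.9%
- 50% Higher: 7.9 + 10.7 + 29.5 = 48.1%

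The range is 48% to 72%, not 49% to 72%. In 50% Higher, the printed selection of doses at or above 33% is 24.5 + 5.4 + 0.2 = 30.1%, and no MTD is 21.8%.

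**2. Reconstruction.** Inputs: Table 1 and Table 3 priors; the Section 2.1 copula with m = n = 1; lead-in likelihood on p_i and combination likelihood on p_ij; overdose cut-offs of 25% and 35%; Section 3.1 limits; 100% cap on dose increases; lower-of-two rule; no combination treatment after a lead-in DLT; lead-in rates from the Table 4 By Prior row.

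Assumptions, because the documents do not settle them:
- Interaction prior: three readings. Section 2.2.3 gives a mean of 1.1 and a 97.5th percentile of log 3 = 1.0986, which cannot both hold.
- Nivolumab 480 mg: entered as 6 mg/kg (480/80 at an assumed 80 kg) or as 3 mg/kg (the same dose rate per 2 weeks).
- True rates at 12.5 mg: 1% in the lead-in; 11%, 14%, 16.5% and 38% in combination (additive, 25% higher, 50% higher, all-toxic).
- All-toxic rates at 25 to 600 mg: 40, 45, 50, 55, 60, 65%.

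This makes 3 x 2 = 6 variants, with 1,000 trials per setting (error about 3 points).

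| Outcome | Start | No lead-in data | Lead-in carried forward | Printed |
|---|---|---|---|---|
| Additive, correct | 25 mg | 74-77% | 80-89% | 71.8% |
| Additive, correct | 12.5 mg | 64-68% | 74-83% | none |
| 25% Higher, correct | 25 mg | 63-71% | 73-78% | 64.9% |
| 50% Higher, correct | 25 mg | 51-58% | 38-48% | 48.1% |
| 50% Higher, 200 mg chosen (true 34%) | 25 mg | 22-26% | 30-43% | 24.5% |
| 50% Higher, 400-600 mg chosen | 25 mg | 5.2-7.0% | 4.5-9.6% | 5.6% |
| 50% Higher, 200 mg chosen | 12.5 mg | 18-20% | 24-40% | none |
| 50% Higher, 400-600 mg chosen | 12.5 mg | 2.4-3.4% | 2.8-6.3% | none |
| All-toxic, trial stops, 3 mg/kg | 25 mg | 74-75% | 42-59% | none |
| All-toxic, trial stops, 6 mg/kg | 25 mg | 66-67% | 70-75% | none |
| All-toxic, trial stops, 3 mg/kg | 12.5 mg | 65-67% | 46-51% | none |
| All-toxic, trial stops, 6 mg/kg | 12.5 mg | 65-74% | 59-73% | none |

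**3. Separate rebuilds.** One used 3 mg/kg and 3,000 trials per setting. With lead-in data from 12.5 mg, correct selection was 88.7 / 78.3 / 46.6% (additive / 25% / 50% higher). Without lead-in data from 25 mg it was 76.3 / 72.6 / 49.2%. In 50% Higher, selection of doses at or above 33% went from 33.1% to 49.4%, and no MTD from 17.7% to 4.0%. A second rebuild in four variants gave 47-58% correct in 50% Higher from 12.5 mg, and a fall of only 1-13 points from a 25 mg start. With the 12.5 mg start, 12.5 mg itself (16.5%) counts as in target, so comparison with 48.1% is not like for like.

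**4. Fit to the printed results.** Without lead-in data in 50% Higher, mean N is 15.2-15.4 (printed 15.5) but no MTD is 14-16% (printed 21.8%). For the Section 4 worked example, 400 mg is recommended and 600 mg excluded, as printed; the target probability is 30-35% (printed 27%). The in-house code therefore differs in some detail.

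**5. Decisions with clean lead-ins.**
- 2/4 combination DLTs in the first cohort at 12.5 mg. With lead-in data, the probability of overdosing at 12.5 mg is 19-32% in five variants, so the dose stays open, and 35.3% in the sixth. Without lead-in data it is 38-45%, a stop in all six. The chance of exactly 2/4 is 6 x 0.165² x 0.835² = 11% at a true 16.5%, and 6 x 0.38² x 0.62² = 33% at a true 38%.
- 4/4 at 100 mg after 0/4 at every lower dose. The probability of overdosing is 10-26% with lead-in data (100 mg stays admissible) and 47-51% without (excluded). This path is rare: about 0.1% at the 50% Higher rates from 25 mg.

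**The case against.** The plan discloses both gaps: Section 2.2.1 calls the simulated prior illustrative, and Section 10.1.1 says that the simulations begin at 25 mg. Section 3.2.2 limits its claim to the scenarios studied. The model only recommends; Section 5.1.2.1 requires agreement on all available data, and Section 4 supplies updated posterior plots. The assumed all-toxic case is severe: 40% against the additive 12% at 25 mg is an odds ratio of (0.40/0.60)/(0.12/0.88) = 4.9, while Section 2.2.3 places a 3-fold increase at its upper percentile. Section 3.3.2 reports few DLTs with other IDO1 inhibitors plus nivolumab.

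Most of this stands as a limit on consequence. Disclosure, however, does not make Table 5 describe the planned model. Lack of real DLT data is also no obstacle, because simulated trials generate their own, and the Section 4 example already combines lead-in and combination data.

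A reader might go further and infer that the planned model performs worse than claimed, or that full borrowing is unsafe. The documents do not support that. Correct selection rises in the two milder scenarios. In 50% Higher it is not clearly below 48.1% from the planned start, most of the added over-toxic selection is at 200 mg, one point above the 33% boundary, and fewer trials end without an MTD although acceptable doses exist. Nor is staying at 12.5 mg after 2/4 in itself an error.

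**Conclusion.** The mismatch is established from the text: lead-in data, starting dose and scenario set all differ between the planned combination model and Table 5, and the stated low end should read 48%. It should be fixed before the first escalation decision.

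The size is approximate. Under the planned data flow, correct selection is about 80-90% in the additive scenario (74-83% in one set of runs from 12.5 mg), generally higher than printed at 25% higher toxicity (about 70-80%), and roughly 38-58% at 50% higher. Selection of doses with a true rate of at least 33% in that last scenario is about 34-49% against 22-33% without lead-in data; single settings fall somewhat outside both ranges. The all-toxic stop rate falls materially only if nivolumab is entered as 3 mg/kg. All these figures rest on the assumed interaction prior, dose conversion and 12.5 mg rates, and on a rebuild that matches the printed results imperfectly.

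**What to change.** Before the first escalation decision:
1. Re-run Table 5 from 12.5 mg, with lead-in DLTs simulated and carried forward as Section 2.2.1 plans, under the lower-of-two rule.
2. Add a scenario with every combination dose too toxic and clean lead-ins.
3. Tabulate the model's decision for each number of DLTs out of each cohort size, from 12.5 mg upward. The Section 4.1 flow chart begins after 25 mg.
4. Restate the Section 3.2.2 conclusion from the re-run. If the old range is kept for reference, correct 49% to 48%.

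The cost is simulation time with existing in-house code and revised appendix text; sample size, visits and eligibility do not change.

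Discounting the lead-in marginal is not part of this fix. It is worth considering only if the re-run shows that clearly excessive results, such as 4/4, remain admissible, and it is a trade-off. In the six variants, half weight excludes 100 mg after 4/4, but additive correct selection from 12.5 mg is 70-74% instead of 74-83%, and the all-toxic stop rate is still only 51-70%.

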2.2.2 Marginal Prior Derivation for Nivolumab Parameters ($\log(\alpha_2)$, $\log(\beta_2)$)

Similar to BMS-986242 monotherapy in the monotherapy phase, the logistic model for nivolumab is as follows:

$$\text{logit}(q_j) = \log(\alpha_2) + \beta_2 \log(d_{2j}/d_2^*),$$

where q_j is the probability of toxicity at dose level d_{2j} . Note that the α_2 and β_2 parameters are assumed positive, and d_2^* is the reference dose for nivolumab.

The toxicity profile of nivolumab has been studied in several studies. A bivariate normal prior for the nivolumab model parameters ($\log(\alpha_2)$, $\log(\beta_2)$) was obtained by extracting a posterior of nivolumab using DLT and safety data from the Study CA209003, which is used later as the meta-analytical-predictive (MAP) prior for nivolumab.

The MAP prior for the model parameters ($\log(\alpha_2)$, $\log(\beta_2)$) was obtained in the following steps.

First, a prior distribution for nivolumab was developed:

- The median DLT rate at the reference dose (3 mg/kg every 2 weeks) was assumed to be 10%, that is, mean ($\log(\alpha_2)$) = $\text{logit}(1/10) = \log(1/9) = -2.197$.
- A doubling in dose was assumed to double odds of DLT, that is, mean($\log(\beta_2)$) = 0.
- The standard deviation of $\log(\alpha_2)$ was set to 2, and the standard deviation of $\log(\beta_2)$ to 1, which allows for considerable prior uncertainty for the dose-toxicity profile.
- The correlation between $\log(\alpha_2)$ and $\log(\beta_2)$ is assumed to be 0 (assuming independence of $\log(\alpha_2)$ and $\log(\beta_2)$).
- In addition, heterogeneity between the historical study and current study was incorporated using a meta-analytic predictive approach by defining between-trial standard deviations τ_1 and τ_2 for $\log(\alpha_2)$ and $\log(\beta_2)$, respectively. The between-trial variability is assumed to be

moderate. Therefore, τ_1 and τ_2 were set to follow a log-normal distribution, with mean $\log(0.25)$ and $\log(0.125)$, respectively, with a common standard deviation $\log(2)/1.96$.

With this prior, the clinical trial data below (Table 2) were used to generate the posterior for nivolumab, which is then used as the MAP prior for this study (Table 3).

Table 2: Data From Single-agent Nivolumab (Study CA209003)

Dose of Nivolumab (mg/kg)	Every 2 Weeks
	No. of DLTs/No. of Evaluable Participants in the Escalation Phase
0.1	0/3
0.3	0/3
1	0/3
3	0/3
10	1/6

Abbreviation: DLT = dose limiting toxicity.

Table 3: Marginal Prior Distribution for Model Parameters for Nivolumab (ie, Posterior from MAP Method)

Parameter	Means	Standard Deviations	Correlation
$\log(\alpha_2), \log(\beta_2)$	(-3.269, -0.152)	(1.186, 0.771)	-0.369

Note: Nivolumab prior information was based on a milligram-per-kilogram dosing instead of flat dosing. If real PK data from this study show difference from the milligram-per-kilogram assumption, the nivolumab prior will be revisited and modified accordingly.

2.2.3 Prior for Interaction Parameters for Joint Toxicity of BMS-986242 and Nivolumab Combination

A gamma prior distribution for the interaction parameter γ_1 is derived to reflect the current uncertainty about the toxicity profile of the combination of BMS-986242 and nivolumab. Although no PK drug-drug interaction is expected, the possibility of a significant positive interaction between BMS-986242 and nivolumab cannot be totally excluded. The interaction parameter γ_1 was chosen accordingly but with a degree of uncertainty to allow for the possibility that the interaction may be positive or negative. Therefore, the following assumptions are made for the interaction parameter:

- γ_1 follows a gamma distribution and with a mean centered at 1.1, which means the combination of 2 agents is likely to have only a small synergistic effect.
- The 97.5 percentile of γ_1 is $\log(3)$, that is, a 3-fold increase in odds of DLT due to the interaction over independence at the starting dose of the combination.

This model assigns the highest probability to there being small synergistic interaction and also allows for the potential of larger synergism of the toxic profiles. It also does not completely ignore the possibility of antagonism because there is a 40% prior probability that γ_1 is less than 1.

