3 DECISION RULE FOR DOSE ESCALATION AND SIMULATION

Dose escalation recommendations for BMS-986242 monotherapy and in combination with nivolumab will be based on the inference from the Bayesian posterior and the probability that the true DLT rate for each dose lies in 1 of the following categories:

- [0%, 16%) under-dosing
- [16%, 33%) targeted toxicity
- [33%, 100%] excessive toxicity

These boundaries are similar to the toxicity boundaries used by a rule-based design (ie, 3 + 3 design) in that a minimum is set at 16% (about 1 in 6) DLT rate and a maximum at 33% (about 2 in 6) DLT rate. Following the principle of EWOC, dose recommendations for the next cohort will be based on the Bayesian model after DLT information becomes available during the DLT period, accounting for all of the available data from the administered doses, and the candidate doses are the ones fulfilling the overdose criterion that there is less than 25% (for monotherapy) and 35% (for combination therapy) chances of excessive toxicity. Only the candidate doses will be considered for the next cohort. While the Bayesian model will use DLT information from the DLT period only, clinical assessment will take into consideration of the totality of available data including PK/Pharmacodynamics from all treated participants.

The MTD is the highest administered dose not expected to cause DLT in more than 33% of the treated participants during the DLT period. The final recommended MTD/RP2D will be based on the recommendation from the BLRM/BLRM-copula, and on an overall assessment of all available safety, PK/Pharmacodynamic, and efficacy data.

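### The interaction prior in Appendix 7 Section 2.2.3 contradicts itself: no gamma distribution has mean 1.1, a 97.5th percentile of log(3) and 40% below 1, and γ₁ = log(3) is not a 3-fold increase in DLT odds

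*Combined protocol and SAP*

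**What the plan says.** Appendix 7 Section 2.1 combines the two single-agent DLT rates through a copula-type formula in which γ₁ "characterizes the drug-drug interactive effect". With m = n = 1 the formula is

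p_comb = 1 − exp(−[{−log(1−p)}^(1/γ₁) + {−log(1−q)}^(1/γ₁)]^γ₁),

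so γ₁ = 1 is independence.

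Section 2.2.3 specifies the prior for γ₁ in four statements:

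- It "follows a gamma distribution and with a mean centered at 1.1".
- Its 97.5th percentile is log(3), explained as "a 3-fold increase in odds of DLT due to the interaction over independence at the starting dose of the combination".
- On where the prior mass falls, the section states: "This model assigns the highest probability to there being small synergistic interaction". It adds that larger synergism is left possible.
- Antagonism is not ruled out, because "there is a 40% prior probability that" γ₁ is below 1.

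The documents give no shape or rate for this gamma. Section 3.1 says the combination model was run in in-house code. Section 3 then uses that model to admit only doses with less than "35% (for combination therapy) chances of excessive toxicity".

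**The concern.** The natural logarithm of 3 is 1.0986. A 97.5th percentile just below the mean is not what a prior centred on weak synergy with room for more would have, and it does not sit with 40% of the mass below 1. The 3-fold gloss would be right if γ₁ were a log odds ratio, since exp(log 3) = 3, but in the Section 2.1 formula it is an exponent.

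Section 2.2.3 is the only specification of the interaction prior in the combination overdose model. If its statements conflict, a reader cannot rebuild the model or tell which prior lies behind the Table 5 operating characteristics. The text also suggests that the prior reaches a 3-fold interaction when the value given does not.

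**Working it through.** **1. Can one gamma meet all three conditions?** Solve the shape k (rate = k/mean) for each pair and check the third.

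| Conditions kept | Result | Third condition |
|---|---|---|
| Mean 1.1; P(γ₁<1) = 0.40 | shape 13.51, rate 13.51/1.1 = 12.28, mode 12.51/12.28 = 1.02, SD 0.30 | 97.5th percentile 1.76; P(γ₁ < log 3) = 53% |
| 97.5th percentile log 3; P(γ₁<1) = 0.40 | shape 541, SD 0.04 | mean 1.01, not 1.1 |
| Mean 1.1; 97.5th percentile log 3 | degenerate: shape 0.0054, SD 14.9, median about 0 | P(γ₁<1) = 97.5%, not 40% |

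Rounding does not explain it: a mean of 1.05 to 1.15 with 39.5% to 40.5% below 1 gives a 97.5th percentile of 1.39 to 2.13. Reading the percentile as 3 instead of log(3) fails too: with mean 1.1 it puts 54% below 1 (shape 2.12), or 97% at a second, degenerate solution.

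**2. What does γ₁ = log(3) do in the copula?** Inputs:

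- BMS-986242 rate from the Table 1 prior means, p = expit(−0.847 + log(d/600)): 0.89% at 12.5 mg and 1.75% at 25 mg. Both doses are shown because the protocol body starts at 12.5 mg and Appendix 7 Section 4.1 at 25 mg.
- Nivolumab rate q: 3.7% = expit(−3.269) from Table 3, assuming that 480 mg every 4 weeks maps to the reference dose, up to 10%, the initial median in Section 2.2.2. The mapping has to be assumed because "Nivolumab prior information was based on a milligram-per-kilogram dosing instead of flat dosing".

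Worked case, 12.5 mg and q = 3.7%: −log(1−p) = 0.00889 and −log(1−q) = 0.0373. At γ₁ = 1 the combined rate is 4.52%; at γ₁ = log(3) it is 4.74%. Odds ratio = (0.0474/0.9526)/(0.0452/0.9548) = 1.05.

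| Dose | q | Rate, independence | Rate, γ₁ = log 3 | Odds ratio | γ₁ needed for 3-fold odds |
|---|---|---|---|---|---|
| 12.5 mg | 3.7% | 4.5% | 4.7% | 1.05 | 2.73 |
| 12.5 mg | 10% | 10.8% | 11.1% | 1.03 | 2.98 |
| 25 mg | 3.7% | 5.4% | 5.7% | 1.07 | 2.57 |
| 25 mg | 10% | 11.6% | 12.0% | 1.05 | 2.73 |

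A true 3-fold odds increase at 12.5 mg would mean a DLT rate of 12.4% (q = 3.7%) to 26.6% (q = 10%). The conclusion does not hang on the chosen rates: for any pair of marginals, the cumulative hazard under γ₁ = log(3) exceeds that under independence by a factor of at most 2^(log 3 − 1) = 1.071.

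**3. Does the choice of prior change decisions?** Illustrative rebuild: importance sampling with 1,000,000 draws from the Table 1 and Table 3 priors (480 mg at the reference dose), overdose defined as a combination rate of at least 33%, no monotherapy DLTs, and the 100% step limit applied. Three priors:

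- A: shape 13.5 (mean 1.1 and 40% kept).
- B: shape 541 (log 3 and 40% kept).
- C: shape 2.75 (mean 1.1 with 97.5th percentile 2.73, a true 3-fold limit at 12.5 mg).

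| Pattern | Dose assessed | Overdose probability A / B / C |
|---|---|---|
| Section 4 example: 0/3 and 0/3 at 25 mg | 400 mg | 26 / 24 / 27% |
| Same | 600 mg | 44 / 42 / 45% |
| 2/3 combination DLTs at 12.5 mg | 12.5 mg | 30 / 28 / 35% |
| 2/3 combination DLTs at 200 mg, lower doses clean | 400 mg | 36 / 34 / 40% |

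The Section 4 example gives the same model output under all three. Over 16 patterns the shift from A was at most about 3 points for B and 6 points for C. The 35% limit was crossed in a way that changed the output in one pattern for each. The 12.5 mg result for C sits on the limit (35.0% to 35.4% over three seeds); using the q = 10% version of the 3-fold limit (shape 2.16) gives 37%.

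**The case against.** The two errors themselves are not disputable; the case against concerns attribution and size.

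- **Which number is misprinted is not settled.** Keeping log(3) and 40% gives a mean of 1.01, so 1.1 could be a slip for 1.01. That would reconcile the three numbers. It would not repair the 3-fold gloss, and an SD of 0.04 leaves no room for the larger synergism that the section says it allows. The log(3) bullet remains the likelier fault, but the sponsor has to say.
- **The rebuild does not reproduce the plan's own example.** Section 4 reports a 27% target probability at 400 mg; the rebuild gives about 30% to 31%. Section 4 reads 600 mg as the dose with a median DLT rate of 0.33; the rebuild gives 0.28 to 0.29. These gaps are about as large as the differences between priors.
- **The 35% crossings are fragile.** If 480 mg maps to twice the reference dose, the 12.5 mg pattern becomes 44/42/47% and all three priors exceed the limit. Table 5 (12% at 25 mg, against 2% alone in Table 4) also implies a nivolumab rate near 10%, well above the 3.7% at the centre of the rebuild.
- **A prior was evidently coded and run for Table 5.** No coding error has been shown; what is shown is a defect in the written specification.
- **Other safeguards apply.** Section 5.1.2.1 takes the lower of the two models' doses, caps steps at 100% and adds clinical review.

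The second to fourth points stand as limits on the decision figures, which should be read as illustrations only. The fifth keeps the practical impact modest. None of them removes the contradiction or makes log(3) a 3-fold odds increase.

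**Conclusion.** The concern holds. The first part is pure arithmetic: the three stated properties fit no gamma distribution, and with mean 1.1 and 40% below 1 only 53% of the prior lies under log(3), not 97.5%. The second is that γ₁ = log(3) raises DLT odds 1.03- to 1.05-fold at 12.5 mg (1.05- to 1.07-fold at 25 mg) for nivolumab DLT rates of 3.7% to 10%. A 3-fold increase needs γ₁ of 2.7 to 3.0 at 12.5 mg (2.6 to 2.7 at 25 mg).

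As written, the prior cannot be implemented without discarding one statement, and the documents do not say which one the code discards. The likely effect on escalation is modest, and which DLT patterns would cross the 35% limit depends on how 480 mg is mapped to the nivolumab reference dose. It should be fixed because this text specifies part of the combination overdose model.

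**What to change.** Replace the log(3) bullet in Section 2.2.3 with the gamma shape and rate actually coded, and give the matching 97.5th percentile on the copula scale. Then bring the mean, the 40% statement and the description of the prior into line with those values. Which intent to keep is the sponsor's choice:

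- **Keep mean 1.1 and 40% below 1:** shape about 13.5, rate about 12.3, 97.5th percentile about 1.76. That is an odds ratio over independence of about 1.4 to 1.6 at 12.5 mg (1.5 to 1.7 at 25 mg).
- **Keep mean 1.1 with a true 3-fold upper limit at 12.5 mg:** shape about 2.2 to 2.75 and mode about 0.6 to 0.7. The 40% then becomes about 52% to 54%, and the statement that weak synergy is most probable has to change.

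Confirm which prior produced Table 5. The cost is one bullet and a check of the existing code; Table 5 needs re-running only if the coded prior differs from the corrected text.
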